1.0. Research Strategy: Significance

Statement of the Problem: Sexually transmitted infection (STIs), alcohol, and drug use are common and critical interrelated factors that are associated with negative consequences for the mother and fetus. There are virtually no empirically supported interventions that are tailored to specifically address these growing public health concerns together during pregnancy. Based upon our encouraging R21 findings, we now propose to test a brief computer-based intervention to fill this critical healthcare gap for a vulnerable, high-risk population.

1.1. STIs are an urgent public health concern for childbearing women

STIs are at a record high in the United States, and STI risk is an increasingly critical and costly health problem for American women, especially for pregnant women who can transmit the infections to their babies. STIs among women are associated with significant morbidity and mortality, including premature death. The American Congress of Obstetricians and Gynecologists (ACOG) and Centers for Disease Control and Prevention (CDC) reported that over the past decade, childbearing women have comprised one of the most rapidly expanding group infected by STIs, including HIV, in the U.S., and this epidemic is “accelerating in young women” Nearly 25% of pregnant women are infected with one of four STIs. Among those who had been treated for an STI in the past 6 months, 30% tested positive for a current STI during their pregnancy. Critical to this trend is the intersection of STIs and alcohol/drug use – both highly prevalent among women.

1.2. STIs and alcohol/drug use during pregnancy lead to significant biomedical risks to woman and fetus

A pregnant woman carries a risk of transmitting an STI to her infant during pregnancy, delivery, or breast-feeding, especially if untreated. STIs such as chlamydia and gonorrhea can be transmitted from the mother to her infant during the delivery, what the CDC laments as a “tragic systems failure.” Adverse effects of prenatal STIs can include miscarriage, ectopic pregnancy, stillbirth, low birth weight, neurological damage, and neonatal sepsis. Illicit drug use also has major health consequences for the pregnant women that can in turn negatively affect fetal development, rates of STIs, depression, intimate partner violence, as well as significant prenatal and neonatal complications (e.g., neurobehavioral and congenital abnormalities). Recent reviews suggest infants whose mothers used marijuana during pregnancy, compared to those who did not, were more likely to have lower birth rates and require neonatal intensive care. Prenatal alcohol exposure can lead to a wide range of adverse effects, known as Fetal Alcohol Spectrum Disorders (FASD) with an estimated 12,000 infants born with FAS each year, and up to three times as many have alcohol-related problems.

1.3. The intersection of STI and substance use disorders in the lives of pregnant women

The Healthy People 2020 objectives include increasing abstinence from alcohol/illicit drug use among pregnant women. Past year prevalence of all illicit drug use was 5.4% for pregnant women. There has been a dramatic national five-fold increase in opiate use during pregnancy, leading to a surge in the incidence of neonatal abstinence syndrome (NAS) of 383% over the past decade. NAS is a postnatal drug withdrawal syndrome and includes central nervous system irritability. Marijuana use during pregnancy is also on the rise, increasing by 62% over the past decade. Nearly 12% of pregnant women reported using marijuana in the past year, in part due to an increased perception of the safety of marijuana use during pregnancy. Regarding alcohol use, 19% of women in their first trimester of pregnancy report using alcohol, and 3% report binge drinking (4 or more drinks in a row). Since underreporting during pregnancy can be substantial, the actual proportion of women drinking during pregnancy is even higher. The co-occurrence of alcohol and substance use and sexual risk taking contribute significantly to STI acquisition, particularly in high-risk and vulnerable populations. Regardless of partner status, monogamous pregnant women who use alcohol or substances are more likely to engage in sexual risk behaviors than their non-pregnant counterparts, and they are five times less likely to use condoms than their non-pregnant counterparts. The use of alcohol/drugs increases the probability for sex risk behavior through disinhibition and impairment of judgment, making the case for addressing these behavior risks together.

1.4 Critical need to address these risks together during pregnancy Despite the escalating rates of substance use during pregnancy, and that co-occurrence with sex risk behavior contributes significantly to STI acquisition, **there are currently no brief interventions that target both of these risks simultaneously during pregnancy.** The extant literature includes computer-

based interventions with a single focus either on improving sexual health, or reducing alcohol/drug use, and very few of these have targeted pregnant women exclusively. A recent brief intervention study identified alcohol use as a critical factor in reducing sex risk behaviors, suggesting the importance of implementing this target in STI preventive interventions, however, it excluded pregnant women.⁹ A review by the U.S. Preventive Services Task Force concluded that “methodologically rigorous trial evidence” is lacking for pregnant women. Ondersma and colleagues are currently testing a brief computer-delivered intervention targeting marijuana use during pregnancy; however, it does not address sex behavior risk. Existing computer-delivered brief motivational interventions for multi-risks (e.g., alcohol/drug use, dating violence, and/or HIV risk behavior) have primarily targeted students and male and female patients presenting to the emergency department, excluding pregnant women. Recent meta-analysis has indicated the superiority of targeting multiple health behaviors rather than just focusing on one behavior. The advantage of fewer sessions, if efficacious, increases the potential feasibility of implementation in a wide variety of settings – and the overall impact is greater when accessible and disseminable to larger populations.

1.5. Pregnancy and postpartum period: a critical time to intervene Given the highly unique set of concerns for this subset of women, including 1) a dramatic national increase in the number of women misusing opioids during pregnancy, leading to a surge in the incidence of neonatal abstinence syndrome (NAS) of 383% over the past decade, 2) marijuana use is on the rise during pregnancy, increasing by 62% over the past decade (and low awareness of the associated health risks for the developing fetus), 3) low rates of condom use during pregnancy; STIs at record high for childbearing women, 4) tremendous health risks and adverse consequences to woman, fetus, and newborn, 5) lack of access to child care services, and 6) the challenges of social stigma, shame and guilt that can be significant for pregnant women who struggle with their substance use, there is a clear need for an intervention tailored to these unique needs of pregnant women. Because the majority (97%) of pregnant women receive at least some prenatal care, the CDC and ACOG have identified the perinatal period as an urgent time for STI prevention and subsequent behavior change, including substance use, to reduce risk for acquiring infection. Further, postpartum women are vulnerable to increased risk of STIs associated with high-risk sexual behaviors including inconsistent condom use and prevalence of alcohol use – with national data suggesting prevalence rates as high as 30-49% -- and drug use prevalence in the range of 4-9%. Recently, the NIH issued a strong recommendation for physicians to advise pregnant women to avoid marijuana use, with growing concerns of its use by women to treat nausea during pregnancy. To optimize postpartum care, the ACOG has recommended proactively addressing both risky health behaviors during pregnancy given that as many as 46% of women in the U.S. do not receive postpartum care, and only 21% receive routine STI screening. There is thus a tremendous opportunity and a clear need to advance clinical care in this important area, especially during the antenatal period.

1.6. Use of a computer-based, brief motivational intervention is ideally suited for target population

A computer-delivered brief intervention is a self-directed, low cost intervention that has several notable strengths for working with women in the perinatal period. The use of computer-assisted self-interview in disclosure of STI/HIV risk has been empirically supported in terms of encouraging the disclosure of sexual risk-taking and additional STI testing without increasing the rate of STI diagnosis, and very few studies have assessed computer-based STI prevention interventions exclusively in women. In computer-delivered intervention trials using the software we propose here, perinatal participants and participants in general have found receiving the MI intervention acceptable and highly likeable, suggesting that a high proportion will engage with the intervention and return for follow up assessments. Over the past decade, interactive technology for alcohol and other substance use disorders have been available and supported by clinical trials. In the extant literature, technology-based interventions for substance use demonstrate that while the effect of these interventions are again mild-moderate in size, there are positive aggregate effects in meta-analyses that can have meaningful public health impact given their overall low cost and potential reach. Further the reach and impact is magnified, as there is potential to aid both the participant and the fetus.

1.7. Role of economic data to inform clinical and policy decisions on resource allocation

Economic data plays a key role in understanding the relative value of costs and benefits associated with a new health intervention and is critical for future dissemination and implementation. Many preventive interventions do not save money, but require a net investment in health resources to yield additional benefits. Implementation decisions will typically consider disease burden, intervention safety and efficacy, resource use, cost-effectiveness, as well as related factors such as feasibility. The pace of health spending has continued to increase as health reform efforts are aimed at slowing the growth in health expenditures. It is critical that data be available to evaluate the costs and benefits of any new interventions such as the proposed HCEM, Health Check-up for Expectant Moms, an innovative computer-delivered screening and brief intervention (SBI) program tailored for high-risk, non-treatment seeking pregnant women. Economic evaluations can provide information to clinical and policy decision makers on prioritization. Evaluation of resource utilization and costs can also inform feasibility and scale-up considerations for the implementation of HCEM.

Summary of scientific premise: In summary, there are several converging lines of data that support the scientific premise of this proposal. STIs as well as alcohol and drug use are common and critical interrelated factors that are associated with negative consequences for the mother, fetus, and infant. Despite the clear risks of STIs among pregnant adult women, very few STI-focused interventions have specifically targeted this group of women and there are currently no brief interventions that target both of these risks simultaneously to address the unique needs of pregnant women, including health risks to their unborn children. The proposed project will test an innovative, high-reach, easily implementable, low-cost computer-delivered intervention, *HCEM*, which is theoretically driven and will address known barriers in early intervention with at-risk women throughout pregnancy and will extend to the postpartum period. A fully powered trial of the HCEM optimized to extend impact to the postpartum period is necessary to determine efficacy. Given that these risks peak during childbearing years and extend into postpartum period, if this promising intervention of high public health significance is found efficacious, it can be readily integrated into prenatal health care settings and thus reduce the risk for adverse outcomes for very large numbers of vulnerable women and infants.

Importance of the Knowledge to be Gained

STI risk and alcohol/drug use are highly prevalent problems in the lives of pregnant women, in particular. Both are associated with physical, psychological and emotional impairment for the woman, serious negative consequences for the developing fetus, and have been shown to increase the cost of health care during pregnancy. Despite the serious morbidity associated with these health concerns, few women are being screened for both STIs and alcohol/drug use during pregnancy: only one third of women are assessed for alcohol use during prenatal care visits. Further, there are few interventions that address either of these critical issues during pregnancy, and virtually none that target both STI risk and alcohol/drug use during pregnancy simultaneously. The information gained through this research will help us to develop and empirically evaluate the efficacy of an intervention for this population. If our intervention proves to be efficacious, this would enable professionals in primary and prenatal care or other settings to have a meaningful impact on STI risk and alcohol/drug use within their setting. Further, there is promising evidence that the application of brief interventions to women in the prenatal period offers substantial benefits to both the woman and her unborn child. The paucity of research targeting both of these health risks together during pregnancy, and the potential success of implementing a computer-based brief intervention in this population invites the proposed research investigation.

2.0. Innovation The theoretical, methodological and clinical innovation of HCEM improves upon current literature in significant ways, specifically: 1) HCEM is innovative because we are targeting the unique needs of pregnant women early in pregnancy who endorse **both** risk for unsafe sex and alcohol/drug use – common, problematic, dual concern for pregnant women that has not typically been addressed concurrently; 2) HCEM is brief and it includes booster sessions that are specifically designed for a high-risk study population who are likely to benefit from additional contact as the literature suggests increases in efficacy and promotion of gains with behavioral interventions when boosters are provided, 3) HCEM targets STI risk reduction for the postpartum period as well as during pregnancy, extending and sustaining the impact of intervention; and, 4) we include assessment of key birth outcomes that are affected by STIs and alcohol/drug use.

3.0. Specific Aims

Sexually transmitted infections (STIs) are at a record high in the United States, and STI risk is an increasingly critical and costly public health concern for American childbearing women. STIs and alcohol/drug use are interrelated and common morbidities that have significant direct and indirect relationships with health and functioning over the longer term for mother and fetus. Undetected and untreated STIs can lead to serious long-term consequences for childbearing women including infertility; for pregnant women, STIs can lead to a number of serious health risks including premature birth, low birth weight, increased need for neonatal care, and fetal death. Similarly, there has been a dramatic national increase in substance use during pregnancy, particularly opiate and marijuana use, leading to complications during pregnancy and poorer birth outcomes. Nearly one quarter of pregnant women are infected with an STI, and over 15% report some form of risky alcohol or drug use. Women who abuse substances are disproportionately more likely to engage in risky sexual behaviors that can result in STIs. Because of this intersection between substance use and STIs and because both are clearly associated with poor health outcomes, the ACOG and CDC strongly recommend targeting both risks during pregnancy.

Many challenges prevent the implementation of behavioral treatment programs in prenatal settings, and many women fail to engage in treatment even when it is readily available. These same women, however, may be willing to engage with brief, technology-delivered interventions that are tailored to their unique needs, and these approaches may be more applicable to be disseminated within overwhelmed prenatal care practices. Our team has successfully tested an innovative computer-delivered screening and brief intervention (SBI) program tailored for high-risk, non-treatment seeking pregnant women. Our preliminary results ($n = 50$) indicate that the Health Check-up for Expectant Moms (HCEM) is acceptable and feasible, and is associated with significant reduction in the key outcomes of alcohol or drug use ($OR = 0.15, p = 0.015$), with a trend toward significance in the reduction of unprotected sex ($OR = 0.17, p = 0.12$) during pregnancy.

The objective of this proposed study is to build upon these promising R21 findings by testing whether HCEM, a computer-delivered SBI that simultaneously targets STI risk and alcohol/drug use during pregnancy, reduces antenatal and postpartum risk more than an attention, time, and information matched control condition among pregnant women seeking prenatal care. To meet this objective, we propose a two-group, randomized controlled trial in which a racially diverse sample of 250 pregnant women at risk for STIs and alcohol/drug use are recruited from high-volume prenatal care clinics or through telephone and online methods, and are assigned to either (a) a computer-delivered, single-session brief intervention plus two booster sessions; HCEM; or (b) a computer-delivered control condition. Computer and/or phone-delivered follow-up assessments will occur at 2 and 6 months, and extending to 6-weeks postpartum. Our biometric objective measures include STI incidence (e.g., chlamydia, gonorrhea) and birth outcomes. We propose the following Specific Aims:

Aim 1 (Primary outcomes): To test the hypothesis that HCEM, compared to an attention, time and information matched control condition, will reduce risk of STIs and alcohol/drug use among at-risk pregnant women during pregnancy at 2 and 6-months follow-up.

- (a) HCEM, as compared to control, will result in fewer unprotected sexual occasions;
- (b) HCEM, as compared to control, will result in lower alcohol use and illicit drug use, and fewer heavy episodic drinking days.

Aim 2 (Secondary outcomes): To test the hypothesis that HCEM will be associated with key secondary outcomes:

- (a) HCEM, as compared to control, will result in fewer STIs (re-infection and/or new infections) during pregnancy and at 6-weeks postpartum;
- (b) HCEM, as compared to control, will result in fewer unprotected sexual occasions and lower alcohol use and illicit drug use at 6-weeks postpartum;
- (c) HCEM, as compared to control, will result in better birth outcomes (e.g., low birth weight);
- (d) To collect and measure resource utilization and costs of HCEM to provide preliminary data to assess feasibility for future implementation and dissemination and to inform practice guidelines.

Aim 3 (Mediation): To explore direct and indirect effects in the above hypotheses:

- (a) To explore the effect of HCEM on the intermediate outcomes of pregnancy-specific knowledge and risk perceptions, autonomous motivation and self-efficacy during pregnancy;
- (b) To test these theory-based mediators of HCEM primary effects hypothesized above.

Impact: This project will fill a critical gap and provide much-needed data on the efficacy and utility of a practical computer-delivered, brief motivational intervention tailored to reach high-risk women during pregnancy and extending impact to postpartum. If this promising intervention is found efficacious, it can be readily integrated into prenatal health care settings and thus reduce the risk for adverse outcomes for very large numbers of vulnerable women and infants.

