Screener items (embedded with general health questions):

1. Questions for history of STI sexual risk (i.e., number of occasions of condomless vaginal (and anal) sex in the past 30 days);
2. T-ACE (four questions) is a screen for risk drinking developed for use in OB/GYN settings;
3. Substance Use Risk-Profile Pregnancy Scale (SURP-P) (three questions) this screening is specifically designed to quickly identify obstetrical patients at risk for alcohol or illicit drug use.

Table 1. Study Measures		Antenatal		Postpartum
Self-report measures	Baseline	19-28 weeks	36-39 weeks	6 weeks
Demographic Information	X			
Marlowe-Crowne Social Desirability – Short Form	X			

Timeline Follow-back, sex, alcohol, drug use	X	X	X	X
Condom Use Self-Efficacy	X	X	X	X
Treatment Self-Regulation Questionnaire	X	X	X	X
HIV/STI Knowledge Questionnaire	X	X	X	X
Risk Perceptions Items (STI)	X	X	X	X
Importance, Readiness, and Confidence Rulers	X	X	X	X
Condom Attitude Scale	X	X	X	X
Perceived Competence Scale	X	X	X	X
COVID-19 Family Stress Screener	X	X	X	X
Objective biometric measures				
Urine or Vaginal Swab Collection: STI Testing	X*	X	X	X
Birth Outcomes				X
Hair Sample Testing (suspended 11/2022)	X**		X**	
Economic and implementation measures				
Costs Analysis	X	X	X	X
Clinic staff surveys	X			

*In-person, Michigan Medicine visits only.

**A urine sample may be collected in place of a hair sample in the event that a hair sample cannot be collected.

The following assessment measures will be administered at the baseline assessment:

1. Demographic information, including age, race, ethnicity, marital/partner status, parity, employment, socioeconomic status.
2. *Marlowe-Crowne Social Desirability Scale-Short*,¹¹⁴ includes 13 items sensitive to social desirability bias.

5.5.2 Primary Outcome Measure:

1. *Unprotected sexual occasions (USOs)* at the 8-week follow-up assessment.

USOs will be obtained from the *Timeline Follow-Back (TLFB)* to assess sex-risk behaviors at baseline and follow up assessments. The TLFB is a calendar assisted structured interview that provides a way to cue memory so that accurate recall is enhanced for event-level data; it has been used to assess sexual risk-taking. USOs will be assessed in the 90 days prior to the baseline, as well as the 8-week follow-up assessments.

5.5.3 Secondary Outcome Measures:

1. *Alcohol use and Illicit drug use*: Self-reported days of alcohol and illicit drug use at 8-week assessment.

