7.0. Data Analysis: Descriptive statistics will be calculated to summarize baseline characteristics for the full cohort and by intervention arm. Quality inspection will be carried out periodically to screen for missing-ness and data anomalies, and entry error. T-tests and chi-square-tests will be used to compare study arms with respect to demographic characteristics and baseline measures of unprotected sex and alcohol/drug use. Any identified confounders with $p \leq 0.10$ will be included in all subsequent analyses. Using the TLFB, we estimate the frequency of number of days in the 90-day period that the participant is engaged in a risky behavior. This will be carried out separately for each of the outcomes, namely, unprotected sex, illicit drug use and alcohol use, and heavy episodic drinking days (Hypothesis 1 and 2). The outcomes will be analyzed under a clustered count regression framework (Poisson or Negative Binomial) with frequency as outcome, and time (baseline, 2 months, 6 months), group (HCEM, control) and time-by-group interaction as the primary covariates. A generalized linear mixed models (GLIMMIX) approach will be adopted assigning a random subject intercept to account for the clustering within each participant. The regression model will be further controlled for potential confounders such as demographic characteristics, social desirability, and other variables that are identified to be significantly associated with outcome in the univariate analyses. We will adjust analyses for baseline pregnancy stage and assessment timing, as well as delivery status (delivered/not delivered) at follow up assessments in our data analysis, and pregnancy loss during course of study (e.g., miscarriage or stillbirth). Changes over time within each group will be estimated post-hoc by sliced effects derived from the regression model. In additional analysis, reduction in proportion of participants engaged in the risky behavior on ≥ 1 days within the 90-day period will be analyzed using a clustered logistic regression with a dichotomous outcome at the subject level indicating the status of the engagement, and with time (baseline, 2 months, 6 months), group (HCEM, control), time-by-group interaction as the primary factors. As before, a random subject intercept will account for the clustering and the model will be controlled for the same ensemble of covariates as in the case of the count regression models. Similar analyses will be conducted in the secondary aims for the outcomes that will be measured postpartum. To test hypothesis 3a and 3b, we will use structural equation modeling (SEM) approach. These include pregnancy-specific measures of autonomous motivation, self-efficacy, knowledge and risk perceptions (see Table 1). These measures are all continuous and will be measured at all three time points. All relevant direct and indirect effects will be evaluated. Significance of the indirect effect of the mediators will be tested using bootstrap method which appears to have good power in small samples. Birth outcome data will be available to the team by accessing patient medical records postpartum (Hypothesis 2c).

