7.3. Missing Data: The missing values at the subject-level will be imputed using multiple imputation (MI) methods. This will use the chained equation method that allows both categorical and continuous variables to be imputed together without making any multivariate joint distributional assumption. We will combine the results from 10 imputed datasets using Rubin's formula.¹³¹ The MI approach is valid for 'Missing at Random' scenario, i.e in cases, where the missing-ness mechanism is independent of the outcome after adjusting for covariates. Refusal to provide hair sample is perhaps one variable for which such an assumption may not be appropriate. Thus, for the models we use the information on hair sample, we will equate refusal with substance use. Based on our improved methodology for hair collection in the R21, we expect to yield $\leq 15\%$ refusal. Given that refusal is likely to be low, impact on results is likely to be small. If refusal exceeds 15%, we will conduct imputation strategies that make various assumptions about missingness and the odds that it represents. Our inability to collect hair and urine samples at remote visits for drug testing (during the COVID-19 pandemic, which began in March 2020 and is currently ongoing as of February, 2023) will result in increased missing data. Because of the difficulties in collecting samples for drug testing due to COVID-19, we suspended all collection of biological samples for drug testing for participants enrolled November 2022 and on.

7.4. Power: We estimated power based on our R21 study and calculated it using extensive simulation. For the count outcomes, power was obtained under a Poisson regression framework with time, group, and time-by-group interaction as covariates. Data was simulated 1000 times from models characterized by time and group specific means as well as the variance of the random effects estimated from the pilot data. Power was assessed for the interaction term as well as the main effects empirically by the proportion of times the corresponding coefficient was deemed statistically significant at 5% level.

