For all the outcomes, our proposed sample of 250 should be adequate for detecting small to moderate effect sizes. Even assuming the worst-case scenario of up to 20% drop-out in both arms, we plan to recruit 125 participants per arm. In our data, we observed reduction in risky behavior in both study arms; however, the reduction in the intervention arm was significantly larger. For example, for unprotected sex, the baseline average number of days of unprotected sex was 36 based on the pilot data. Assuming that the average number of days of unprotected sex drops to 32 and 29 in the control and HCEM groups, respectively, (similar to that obtained in the pilot data) at any of the follow up points, using 100 subjects per arm the difference in the reduction in the groups will be deemed as statistically significant with more than 90% power. We assume a difference of 10 days between the intervention and the control groups in the change from baseline to be clinically significant. The differences for alcohol use and drug use were more prominent in our R21 data and we anticipate to be well powered for these aims. Similar effects were obtained when the dichotomous counter-parts were simulated using a clustered logistic regression model. In our data, more than 95% of the participants at baseline were engaged in risky sexual behavior. In the proposed study, we estimate a drop by 50% in the HCEM arm, which would be statistically significant using the above sample size. Outcomes of binary alcohol/drug use also yield power above 80% for scenarios similar to those obtained in the pilot data.

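### The plan gives two different primary outcome sets, names no deciding contrast, and analyses days of unprotected sex where the primary outcome counts occasions.

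*Combined protocol and SAP*

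**What the plan says.** Aim 1 (section 3.0) carries the label of primary outcomes and sets its time frame as "among at-risk pregnant women during pregnancy at 2 and 6-months follow-up". Part (a) is fewer unprotected sexual occasions. Part (b) is "HCEM, as compared to control, will result in lower alcohol use and illicit drug use, and fewer heavy episodic drinking days". That makes four behaviours at two visits.

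Section 5.5.2 has a singular heading and one item: "Unprotected sexual occasions (USOs)* at the 8-week follow-up assessment". Section 5.5.3 lists as secondary "Self-reported days of alcohol and illicit drug use at 8-week assessment". Heavy episodic drinking appears only afterwards, among the other outcomes.

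Section 7.0 gives each behaviour its own count regression with "time (baseline, 2 months, 6 months), group (HCEM, control) and time-by-group interaction as the primary covariates". For every outcome, including unprotected sex, "we estimate the frequency of number of days in the 90-day period that the participant is engaged in a risky behavior". It gives no significance level for the treatment comparisons.

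Section 7.4 assessed power for the interaction and for the main effects, by how often the "corresponding coefficient was deemed statistically significant at 5% level". Its worked example is in days: "the baseline average number of days of unprotected sex was 36 based on the pilot data", falling to 32 (control) and 29 (HCEM). It claims power above 90% with 100 women per arm at any of the follow-ups.

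**The concern.** Aim 1 and section 5.5.2 are both current text, and nothing says which governs. A reader holding Aim 1 could report a primary success on drug use at 6 months. A reader holding section 5.5.2 would call the same trial negative if week-8 unprotected sex missed significance. A split of this kind is plausible: in the pilot (section 3.0), substance use gave p = 0.015 and unprotected sex p = 0.12.

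Section 7.0 does not settle it. With three time levels the time-by-group interaction has two degrees of freedom, and it is listed beside the two main effects. The week-8 contrast, the 6-month contrast, the joint interaction or a group effect could each be presented afterwards as the planned test. The unit is open too: two unprotected occasions on one day count as two in section 5.5.2 and as one in section 7.0. That mismatch is confined to unprotected sex.

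**Working it through.** **1. Status of each behaviour**

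| Behaviour | Aim 1 | Sections 5.5.2 to 5.5.3 and following list |
|---|---|---|
| Unprotected sex | primary, 2 and 6 months, occasions | primary, week 8, occasions |
| Alcohol use | primary, 2 and 6 months | secondary, week 8 |
| Illicit drug use | primary, 2 and 6 months | secondary, week 8 |
| Heavy episodic drinking | primary, 2 and 6 months | other outcome |

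Sections 7.0 and 7.4 use days for unprotected sex.

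**2. Power claimed in section 7.4.** Inputs from that section: means 36 at baseline, 32 and 29 at follow-up, n = 100 per arm, 5% level (two-sided assumed). Poisson counts with a random subject intercept, which cancels from within-woman change. Effect: ln(29/32) = −0.0984.

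- Baseline to one follow-up: SE = √[(1/29 + 1/36 + 1/32 + 1/36)/100] = 0.0348; z = 2.83; power = Φ(2.83 − 1.96) = 0.807.
- Baseline to both follow-ups pooled: SE = √[(1/58 + 1/36 + 1/64 + 1/36)/100] = 0.0297; z = 3.31; power = 0.912.
- Joint 2-df interaction, same effect at both visits: noncentrality 3.31² = 10.96; power = 0.851.
- Group difference at one follow-up, ignoring baseline: SE = √[(1/29 + 1/32)/100] = 0.0256; power = 0.970. This holds only with no between-woman variance, because the intercept does not cancel here.

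The figure above 90% is therefore reproduced for the pooled contrast and for the follow-up-only reading. It is not reproduced for the baseline-to-week-8 change, the contrast closest to section 5.5.2. Simulation with assumed intercept variances from 0 to 1 agreed: about 80 to 81% for one follow-up and 91 to 92% pooled.

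**3. False-positive chance if any one Aim 1 contrast sufficed.** Four behaviours × two visits = eight contrasts, each at 5%.

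- Independent: 1 − 0.95⁸ = 0.337.
- Correlated normal statistics, by simulation (the correlations are assumptions):

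| Between behaviours | Between visits | Any of eight significant |
|---|---|---|
| 0.2 | 0.5 | 0.308 |
| 0.2 | 0.7 | 0.286 |
| 0.5 | 0.5 | 0.269 |
| 0.7 | 0.5 | 0.227 |
| 0.7 | 0.7 | 0.209 |

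**4. Chance of opposite answers with no true effect** (another Aim 1 contrast significant, week-8 unprotected sex not). Independent: 0.95 × (1 − 0.95⁷) = 0.287. Correlated: 0.258 at (0.2, 0.5), down to 0.159 at (0.7, 0.7).

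**5. Other readings of Aim 1**

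- One joint interaction test per behaviour, any of four: 1 − 0.95⁴ = 0.185 if independent; about 0.13 to 0.18 over the same correlations.
- Both (a) and (b) required, at any visit and with any (b) behaviour: (1 − 0.95²)(1 − 0.95⁶) = 0.0975 × 0.265 = 0.026 if independent; about 0.02 to 0.06 over the same correlations.

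**The case against.** The strongest reply is that Aim 1 is a single hypothesis worded conjunctively: HCEM reduces both sexual risk and substance use. Nowhere does the plan say that one significant result is enough. If both parts are required, the false-positive chance is roughly 2 to 6%, so there is no inflation. Counting eight contrasts is also a choice; section 7.0 could be read as four joint tests, giving 13 to 19%. Both points stand, so the 21 to 34% range must stay conditional. They also show the problem, since these readings put the error rate anywhere from about 2% to 34% and the plan selects none.

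It can also be said that the interaction is the evident test, because section 7.4 powers a difference in reductions, and that section 5.5.2 supplies the visit. The section 7.0 model can indeed yield that contrast. But no passage joins the two, and section 7.4 says main effects were powered as well.

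The pilot p-values come from 50 women, one booster and a 4-month assessment (section 4.2), not from week-8 counts. They make a split plausible rather than likely. The power figures show no error in section 7.4 either, since its random-effect variance and tested coefficient are not given. They show only that the contrast matters.

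**Conclusion.** The concern holds. Aim 1 and section 5.5.2 disagree on which behaviours and visits are primary, section 7.0 names no deciding test, and the unit for unprotected sex changes between sections. Following the plan as written permits opposite primary conclusions from the same data, so this must be fixed.

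The size depends on the reading. With any of eight contrasts counting, the false-positive chance is 34% under independence and about 21 to 31% under the assumed correlations. With (a) and (b) both required there is no such inflation. For the single section 5.5.2 endpoint it is 5%.

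Power for the section 7.4 scenario runs from 81% (one follow-up) through 85% (2-df interaction) to 91% (pooled). These figures assume Poisson variation with no overdispersion beyond the random intercept. Section 7.0 allows a Negative Binomial model; with an assumed variance inflation of 2, single-follow-up power falls to about 52%.

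**What to change.** Before any by-arm results are seen:

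1. Align Aim 1 and section 7.0 with section 5.5.2. Name one confirmatory test: the HCEM-versus-control contrast at week 8 for unprotected sex, from the section 7.0 model, at two-sided 5%.
2. Make the other behaviours and all 6-month contrasts secondary, either without confirmatory claims or tested in a fixed order after the primary.
3. If several primaries are preferred, list each with its visit and state the success rule and the multiplicity method. As a guide to the cost, Bonferroni over eight tests (0.05/8) lowers power for a single-visit unprotected-sex contrast from 80.7% to 53.7% at 100 per arm.
4. Use one variable, occasions or days, in Aim 1 and sections 5.5.2, 7.0 and 7.4.
5. Check that the section 7.4 power statement applies to that variable and contrast, and restate it if not.

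While defining the week-8 endpoint, settle its window as well: if the 90-day look-back applies at day 56, it reaches 90 − 56 = 34 days before baseline.

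The cost is text edits and perhaps a re-run power calculation, with no new data collection. If occasions are chosen, new inputs are needed because section 7.4 gives only days. The sponsor gives up a primary claim resting on substance use or 6-month results alone or, with several primaries, accepts a stricter per-test level or a fixed order.
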